## 8.0 Dosage Modification Based on Adverse Events

If the patient develops any Grade 2 or higher Adverse Event (AE) attributed to rose geranium in sesame oil nasal spray or isotonic nasal saline, it should be recorded on the AE Form and the study spray should be reduced to once a day or be stopped per clinician discretion. The patient should continue to be followed according to protocol criteria.

## 9.0 Ancillary Treatment/Supportive Care

### 9.1 Full supportive care:

Other treatment as necessary for control of chemotherapy related symptoms is allowed, with the exception of utilization of other topical nasal therapies.

## 10.0 Adverse Event (AE) Monitoring and Reporting

The site principal investigator is responsible for reporting any/all serious adverse events to the sponsor as described within the protocol, regardless of attribution to study agent or treatment procedure.

The sponsor/sponsor-investigator is responsible for notifying FDA and all participating investigators in a written safety report of any of the following:

- Any suspected adverse reaction that is both serious and unexpected.
- Any findings from laboratory animal or *in vitro* testing that suggest a significant risk for human subjects, including reports of mutagenicity, teratogenicity, or carcinogenicity.
- Any findings from epidemiological studies, pooled analysis of multiple studies, or clinical studies, whether or not conducted under an IND and whether or not conducted by the sponsor, that suggest a significant risk in humans exposed to the drug
- Any clinically important increase in the rate of a serious suspected adverse reaction over the rate stated in the protocol or Investigator's Brochure (IB).

Summary of SAE Reporting for this study  
(please read entire section for specific instructions):

WHO:	WHAT form:	WHERE to send:
All sites	
Pregnancy Reporting  http://ctep.cancer.gov/protocolDevelopment/electronic_applications/docs/PregnancyReportFormUpdated.pdf
	
Mayo Sites – attach to MCCC Electronic SAE Reporting Form  http://livecycle2.mayo.edu/workspace/?startEndpoint=MC4158-56/Processes/MC4158-56-Process.MC4158-56
 
Will automatically be sent to [contact] and [contact]
 
Non Mayo sites – complete and forward to [contact]

Mayo Clinic Sites	Mayo Clinic Cancer Center SAE Reporting Form: http://livecycle2.mayo.edu/workspace/?startEndpoint=MC4158-56/Processes/MC4158-56-Process.MC4158-56	Will automatically be sent to [contact] and [contact]
Non-Mayo Clinic Sites	MedWatch 3500A: http://www.fda.gov/downloads/AboutFDA/ReportsManualsForms/Forms/UCM048334.pdf	[contact] and [contact]

### Definitions

*Adverse Event*

Any untoward medical occurrence associated with the use of a drug in humans, whether or not considered drug related.

*Suspected Adverse Reaction*

Any adverse event for which there is a reasonable possibility that the drug caused the adverse event.

*Expedited Reporting*

Events reported to sponsor within 24 hours, 5 days or 10 days of study team becoming aware of the event.

*Routine Reporting*

Events reported to sponsor via case report forms

*Events of Interest*

Events that would not typically be considered to meet the criteria for expedited reporting, but that for a specific protocol are being reported via expedited means in order to facilitate the review of safety data (may be requested by the FDA or the sponsor).

#### 10.1 Adverse Event Characteristics

**CTCAE term (AE description) and grade:** The descriptions and grading scales found in the revised NCI Common Terminology Criteria for Adverse Events (CTCAE) version 5.0 will be utilized for AE reporting. All appropriate treatment areas should have access to a copy of the CTCAE version 5.0. A copy of the CTCAE version 5.0 can be downloaded from the CTEP web site:

([http://ctep.cancer.gov/protocolDevelopment/electronic\\_applications/ctc.htm](http://ctep.cancer.gov/protocolDevelopment/electronic_applications/ctc.htm))

- a. Identify the grade and severity of the event using the CTCAE version 5.0.
- b. Determine whether the event is expected or unexpected (see Section 10.2).
- c. Determine if the adverse event is related to the study intervention (agent, treatment or procedure) (see Section 10.3).
- d. Determine whether the event must be reported as an expedited report. If yes, determine the timeframe/mechanism (see Section 10.4).
- e. Determine if other reporting is required (see Section 10.5).
- f. Note: All AEs reported via expedited mechanisms must also be reported via the routine data reporting mechanisms defined by the protocol (see Sections 10.6 and 18.0).

NOTE: A severe AE is NOT the same as a serious AE, which is defined in Section 10.4.

#### 10.2 Expected vs. Unexpected Events

*Expected events* - are those described within the Section 15.0 of the protocol, the study specific consent form, package insert (if applicable), and/or the investigator brochure, (if an investigator brochure is not required, otherwise described in the general investigational plan).

*Unexpected adverse events* or suspected adverse reactions are those not listed in Section 15.0 of the protocol, the study specific consent form, package insert (if applicable), or in the investigator brochure (or are not listed at the specificity or severity that has been observed); if an investigator brochure is not required or available, is not consistent with the risk information described in the general investigational plan.

*Unexpected* also refers to adverse events or suspected adverse reactions that are mentioned in the investigator brochure as occurring with a class of drugs but have not been observed with the drug under investigation.

An investigational agent/intervention might exacerbate the expected AEs associated with a commercial agent. Therefore, if an expected AE (for the commercial agent) occurs with a higher degree of severity or specificity, expedited reporting is required.

NOTE: \*The consent form may contain study specific information at the discretion of the Principal Investigator; it is possible that this information may NOT be included in the protocol or the investigator brochure. Refer to protocol or IB for reporting needs.

#### 10.3 Attribution to agent(s) or procedure

When assessing whether an adverse event (AE) is related to a medical agent(s) medical or procedure, the following attribution categories are utilized:

Definite - The AE is *clearly related* to the agent(s)/procedure.

Probable - The AE is *likely related* to the agent(s)/procedure.

Possible - The AE *may be related* to the agent(s)/procedure.

Unlikely - The AE is *doubtfully related* to the agent(s)/procedure.

Unrelated - The AE is *clearly NOT related* to the agent(s)/procedure.

#### 10.32 EXPECTED Serious Adverse Events: Protocol Specific Exceptions to Expedited Reporting

For this protocol only, the following Adverse Events/Grades are expected to occur within this population and do not require Expedited Reporting. These events must still be reported via Routine Reporting (see Section 10.6).\*

\*Report any clinically important increase in the rate of a serious suspected adverse reaction (at your study site) over that which is listed in the protocol or investigator brochure as an expedited event.

\*Report an expected event that is greater in severity or specificity than expected as an expedited event.

\*Specific protocol exceptions to expedited reporting should be reported expeditiously by investigators **ONLY** if they exceed the expected grade of the event.

The following hospitalizations are not considered to be SAEs because there is no “adverse event” (i.e., there is no untoward medical occurrence) associated with the hospitalization:

- Hospitalizations for respite care
- Hospitalization planned before informed consent (where the condition requiring the hospitalization has not changed post study drug administration)
- Hospitalization for elective procedures unrelated to the current disease and/or treatment on this trial
- Hospitalization for routine maintenance of a device (e.g., battery replacement) that was in place before study entry

- Hospitalization, or other serious outcomes for signs and symptoms of progression of the cancer.

**10.4 Expedited Reporting Requirements for Commercial or Commercial Imaging Agents (Non-IND) Agent(s) ONLY:**

**10.41 Expedited Reporting Requirements for Adverse Events that Occur in a Non-IND trial within 30 Days of the Last Administration of a Commercial Agent**

**FDA REPORTING REQUIREMENTS FOR SERIOUS ADVERSE EVENTS (21 CFR Part 312)**

**NOTE:** Investigators **MUST** immediately report to the sponsor **ANY** Serious Adverse Events, whether or not they are considered related to the investigational agent(s)/intervention (21 CFR 312.64)  
An adverse event is considered serious if it results in **ANY** of the following outcomes:

- 1) Death
- 2) A life-threatening adverse event
- 3) An adverse event that results in inpatient hospitalization or prolongation of existing hospitalization for  $\geq 24$  hours
- 4) A persistent or significant incapacity or substantial disruption of the ability to conduct normal life functions
- 5) A congenital anomaly/birth defect.
- 6) Important Medical Events (IME) that may not result in death, be life threatening, or require hospitalization may be considered serious when, based upon medical judgment, they may jeopardize the patient or subject and may require medical or surgical intervention to prevent one of the outcomes listed in this definition. (FDA, 21 CFR 312.32; ICH E2A and ICH E6).

**ALL SERIOUS** adverse events that meet the above criteria **MUST** be immediately reported to the sponsor within the timeframes detailed in the table below.

Hospitalization	Grade 1 Timeframes	Grade 2 Timeframes	Grade 3 Timeframes	Grade 4 & 5 Timeframes
Resulting in Hospitalization $\geq 24$ hrs		7 Calendar Days		24-Hour 3 Calendar Days
Not resulting in Hospitalization $\geq 24$ hrs	Not required		7 Calendar Days	

**Expedited AE reporting timelines are defined as:**

- o “24-Hour; 3 Calendar Days” - The AE must initially be reported within 24 hours of learning of the AE, followed by a complete expedited report within 3 calendar days of the initial 24-hour report.
- o “7 Calendar Days” - A complete expedited report on the AE must be submitted within 7 calendar days of learning of the AE.

Serious adverse events that occur more than 30 days after the last administration of investigational agent/intervention and have an attribution of possible, probable, or definite require reporting as follows:

**Expedited 24-hour notification followed by complete report within 3 calendar days for:**

- All Grade 4, and Grade 5 AEs

**Expedited 7 calendar day reports for:**

- Grade 2 adverse events resulting in hospitalization or prolongation of hospitalization
- Grade 3 adverse events

 For studies using PET or SPECT IND agents, the AE reporting period is limited to 10 radioactive half-lives, rounded UP to the nearest whole day, after the agent/intervention was last administered. Footnote “1” above applies after this reporting period.

Effective Date: May 5, 2011

NOTE: Refer to Section 10.32 for exceptions to Expedited Reporting

#### 10.42 General reporting instructions

The Mayo IND and/or MCCC Compliance will assist the sponsor-investigator in the processing of expedited adverse events and forwarding of suspected unexpected serious adverse reactions (SUSARs) to the FDA and IRB.

Use Mayo Expedited Event Report form

<http://livecycle2.mayo.edu/workspace/?startEndpoint=MC4158-56/Processes/MC4158-56-Process.MC4158-56> for investigational agents or commercial/investigational agents on the same arm. Will automatically be sent to [[contact]](mailto:[contact]) and [[contact]](mailto:[contact])

#### Non-MCCC Institutions:

Use form MedWatch 3500A

<http://www.fda.gov/downloads/AboutFDA/ReportsManualsForms/Forms/UCM048334.pdf>

Submit copies to [[contact]](mailto:[contact]), [[contact]](mailto:[contact]) and

#### 10.43 Reporting of re-occurring SAEs

ALL SERIOUS adverse events that meet the criteria outlined in table 10.41 MUST be immediately reported to the sponsor within the timeframes detailed in the corresponding table. This reporting includes, but is not limited to SAEs that

#### 10.5 Other Required Reporting

##### 10.51 Unanticipated Problems Involving Risks to Subjects or Others (UPIRTSOS)

Unanticipated Problems Involving Risks to Subjects or Others (UPIRTSOS) in general, include any incident, experience, or outcome that meets **all** of the following criteria:

1. Unexpected (in terms of nature, severity, or frequency) given (a) the research procedures that are described in the protocol-related documents, such as the IRB-approved research protocol and informed consent document; and (b) the characteristics of the subject population being studied;
2. Related or possibly related to participation in the research (in this guidance document, possibly related means there is a reasonable possibility that the incident, experience, or outcome may have been caused by the procedures involved in the research); and
3. Suggests that the research places subjects or others at a greater risk of harm (including physical, psychological, economic, or social harm) than was previously known or recognized.

Some unanticipated problems involve social or economic harm instead of the physical or psychological harm associated with adverse events. In other cases, unanticipated problems place subjects or others at increased *risk* of harm, but no harm occurs.

Note: If there is no language in the protocol indicating that pregnancy is not considered an adverse experience for this trial, and if the consent form does not indicate that subjects should not get pregnant/impregnate others, then any pregnancy in a subject/patient or a male patient's partner (spontaneously reported) which occurs during the study or within 120 days of completing the study should be reported as a UPIRTSO.

**Mayo Clinic Cancer Center (MCCC) Institutions:**

If the event meets the criteria for IRB submission as a Reportable Event/UPIRTSO, provide the appropriate documentation and use the Mayo Clinic Cancer Center Expedited Event Report form <http://livelcycle2.mayo.edu/workspace/?startEndpoint=MC4158-56/Processes/MC4158-56-Process.MC4158-56>, to submit to [[contact]](mailto:[contact]). The Mayo Clinic Compliance Unit will review and process the submission to the Mayo Clinic IRB and work with the IND Coordinator for submission to FDA.

**Non-MCCC Institutions:**

Submit to your IRB as required by your institutional policies. Submit copies to [FDA, [contact]](mailto:FDA, [contact]) and

**10.52 Death**

**Note: A death on study requires both routine and expedited reporting regardless of causality, unless as noted below. Attribution to treatment or other cause must be provided.**

Any death occurring within 30 days of the last dose, regardless of attribution to an agent/intervention under an IND requires expedited reporting within 24-hours.

Any death occurring greater than 30 days with an attribution of possible, probable, or definite to an agent/intervention under an IND requires expedited reporting within 24-hours.

**Reportable categories of Death**

- Death attributable to a CTCAE term.
- Death Neonatal: A disorder characterized by cessation of life during the first 28 days of life.
- Death NOS: A cessation of life that cannot be attributed to a CTCAE term associated with Grade 5.
- Sudden death NOS: A sudden (defined as instant or within one hour of the onset of symptoms) or an unobserved cessation of life that cannot be attributed to a CTCAE term associated with Grade 5.
  - Death due to progressive disease should be reported as **Grade 5 “General disorders and administration site conditions-Disease progression”** under the system organ class (SOC) of the same name. Evidence that the death was a manifestation of underlying disease (e.g., radiological changes suggesting tumor growth or progression; clinical deterioration associated with a disease process) should be submitted.

**10.53 Secondary Malignancy**

- A **secondary malignancy** is a cancer caused by treatment for a previous malignancy (e.g., treatment with investigational agent/intervention, radiation or chemotherapy). A secondary malignancy is not considered a metastasis of the initial neoplasm.

- All secondary malignancies that occur following treatment with an agent under an IND will be reported. Three options are available to describe the event:
  - Leukemia secondary to oncology chemotherapy (e.g., Acute Myelocytic Leukemia [AML])
  - Myelodysplastic syndrome (MDS)
  - Treatment-related secondary malignancy
- Any malignancy possibly related to cancer treatment (including AML/MDS) should also be reported via the routine reporting mechanisms outlined in each protocol.

#### 10.54 Second Malignancy

A second malignancy is one unrelated to the treatment of a prior malignancy (and is NOT a metastasis from the initial malignancy). Second malignancies require ONLY routine reporting unless otherwise specified.

#### 10.55 Pregnancy, Fetal Death, and Death Neonatal

If a female subject (or female partner of a male subject) taking investigational product becomes pregnant, the subject taking should notify the Investigator, and the pregnant female should be advised to call her healthcare provider immediately. The patient should have appropriate follow-up as deemed necessary by her physician. If the baby is born with a birth defect or anomaly, a second expedited report is required.

Prior to obtaining private information about a pregnant woman and her infant, the investigator must obtain consent from the pregnant woman and the newborn infant's parent or legal guardian before any data collection can occur. A consent form will need to be submitted to the IRB for these subjects if a pregnancy occurs. If informed consent is not obtained, no information may be collected.

In cases of fetal death, miscarriage or abortion, the mother is the patient. In cases where the child/fetus experiences a serious adverse event other than fetal death, the child/fetus is the patient.

NOTE: When submitting Mayo Expedited Adverse Event Report reports for “Pregnancy”, “Pregnancy loss”, or “Neonatal loss”, the potential risk of exposure of the fetus to the investigational agent(s) or chemotherapy agent(s) should be documented in the “Description of Event” section. Include any available medical documentation. Include this form:

[http://ctep.cancer.gov/protocolDevelopment/electronic\\_applications/docs/PregnancyReportFormUpdated.pdf](http://ctep.cancer.gov/protocolDevelopment/electronic_applications/docs/PregnancyReportFormUpdated.pdf)

##### 10.551 Pregnancy

Pregnancy should be reported in an expedited manner as **Grade 3 “Pregnancy, puerperium and perinatal conditions - Other (pregnancy)”** under the Pregnancy, puerperium and perinatal conditions SOC. Pregnancy should be followed until the outcome is known.

##### 10.552 Fetal Death

Fetal death is defined in CTCAE as “A disorder characterized by death in utero; failure of the product of conception to show evidence of respiration, heartbeat, or definite movement of a voluntary muscle after expulsion from the uterus, without possibility of resuscitation.”

Any fetal death should be reported expeditiously, as **Grade 4 “Pregnancy, puerperium and perinatal conditions - Other (pregnancy loss)”** under the Pregnancy, puerperium and perinatal conditions SOC.

10.553 Death Neonatal

Neonatal death, defined in CTCAE as “A disorder characterized by cessation of life occurring during the first 28 days of life” that is felt by the investigator to be at least possibly due to the investigational agent/intervention, should be reported expeditiously.

A neonatal death should be reported expeditiously as **Grade 4 “General disorders and administration - Other (neonatal loss)”** under the General disorders and administration SOC.

10.6 Required Routine Reporting

10.61 **Baseline and Adverse Events Evaluations**

Pretreatment symptoms/conditions other than nasal symptoms do not need to be graded.

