#### 4.0 Test Schedule

Tests and procedures	Active Monitoring Phase		
	≤ 14 days prior to Registration	Baseline (Day 1)	Days 7 and 14
Window			±3 days
History and appropriate physical exam	X		
Adverse event assessment		X	X
Baseline pre-nasal spray questionnaire (App I)		X 	
Nasal symptom and patient experience questionnaire (App II). Nurse should ensure that this contains a record of patient's most prominent nasal symptom at baseline			X
Nurse/research staff call 			X

1. Phone evaluation once weekly, to remind patients to complete questionnaires and evaluate AEs.
2. Administer questionnaire on the same day nasal spray starts, making sure that the patient completes the questionnaire prior to receiving the study spray

Cross-Over Continuation Phase (For Initial Saline participants only)		
Tests and procedures	Baseline (Day 1)	Days 7 and 14 after cross-over
Window	±14 days	± 3 days
Patient contact (Nurse visit/call)	X	
Adverse event assessment		X
Baseline pre-nasal spray questionnaire (App I)	X 	
Nasal symptom and patient experience questionnaire (App II). Nurse/research staff should ensure that this contains a record of patient's most prominent nasal symptom at baseline		X
Nurse/research staff call 		X

1. Phone evaluation once weekly, to remind patients to complete questionnaires and evaluate AEs
2. Administer questionnaire on the same day nasal spray starts, making sure that the patient completes the questionnaire prior to receiving the study spray

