### 6.5 Baseline symptoms

Only nasal symptoms are required to be documented at baseline, within one day prior to starting the spray.

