10.62 All other AEs

Submit via appropriate MCCC Case Report Forms (i.e., paper or electronic, as applicable) the following AEs experienced by a patient and not specified in Section 10.6:

10.621 Grade 1 and 2 AEs deemed *possibly, probably, or definitely* related to the study treatment or procedure.

10.622 Grade 3 and 4 AEs regardless of attribution to the study treatment or procedure.

10.623 Grade 5 AEs (Deaths)

10.6231 Any death within 30 days of the patient’s last study treatment or procedure regardless of attribution to the study treatment or procedure.

10.6232 Any death more than 30 days after the patient’s last study treatment or procedure that is felt to be at least possibly treatment related must also be submitted as a Grade 5 AE, with a CTCAE type and attribution assigned.

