2. When applied nasally, patients may experience a bad taste
3. Instruct patients to report any rash or burning with application
4. Agent should be stored at room temperature

15.2 **Placebo**

A matching isotonic nasal saline spray will be identical in appearance to the Rose Geranium Oil Nasal Spray. The isotonic nasal saline spray will contain 0.9% Sodium Chloride. It will also contain 0.133% of benzalkonium chloride solution 50% per 100ml of normal saline, as a preservative. The nasal spray containers with screw cap closure will be purchased from Professional Compounding Centers of America (PCCA). The contents of each container will be 30 ml. The placebo spray should be stored at controlled room temperature (20°-25 ° C or 68°-77° F), with excursions to 15-30°C (59-86°F) permitted.

15.21 **Optional crossover phase:** Patients initially enrolled on the placebo arm have the option to crossover and receive 2 weeks of the Rose Geranium Oil Nasal Spray.

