The constellation of adverse events (AEs) as scored using the National Cancer Institute Common Terminology Criteria for Adverse Events, v5.0 (CTCAE v5.0) will be summarized within arms by reporting the number and percentage of patients. Specifically, to evaluate the AE profiles associated with each arm, the maximum grade for each type of AE will be recorded for each patient and frequency tables will be reviewed to determine overall patterns and compared between arms using Wilcoxon tests.

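### The between-arm AE comparison ranks Grade 1-2 events kept only if judged related together with Grade 3-4 events kept whatever the cause, and the Day 1 AE assessment it could use is left undefined

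*Combined protocol and SAP*

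**What the plan says.** **Collection (10.62).** Sites submit "Grade 1 and 2 AEs deemed *possibly, probably, or definitely* related to the study treatment or procedure" and "Grade 3 and 4 AEs regardless of attribution to the study treatment or procedure". Deaths follow the unfiltered rule for the first month: "Any death within 30 days of the patient’s last study treatment or procedure regardless of attribution to the study treatment or procedure". Later deaths are submitted only if at least possibly related.

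**Analysis (16.5).** For the AE profile, "the maximum grade for each type of AE will be recorded for each patient". Frequency tables are reviewed and the arms are compared by Wilcoxon tests. No attribution restriction, baseline adjustment, effect size or power is stated for this comparison.

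**Baseline.** The Section 4.0 schedule has a row "Adverse event assessment" marked at Day 1 and again at Days 7 and 14. Section 6.5 says "Only nasal symptoms are required to be documented at baseline, within one day prior to starting the spray". Section 10.61 says "Pretreatment symptoms/conditions other than nasal symptoms do not need to be graded".

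**Effects the protocol names.** Section 15.19 says "When applied nasally, patients may experience a bad taste" and also mentions rash, burning on application and eye irritation. Section 1.0 reports one earlier user with an oily coating in the throat. Section 15.2 claims that the saline matches the oil in appearance. It does not mention taste or texture.

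**The concern.** Toxicity related to the spray is the only secondary goal in Section 2.2. The effects that the protocol names are plausibly mostly Grade 1-2, so they fall in the part of the data that depends on a relatedness judgement. All patients are on chemotherapy, which can produce similar complaints.

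Two things follow. First, the maximum-grade variable is not one ordered scale, because what a zero means depends on an attribution decision. Second, if an oily residue or a taste lets patients or staff guess the arm, background symptoms could be attributed more readily on one side, and the Grade 1-2 part of the comparison would be biased. A usable Day 1 record would help to separate new from existing complaints, but the plan does not say what the scheduled Day 1 assessment should record.

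**Working it through.** **1. The plan's own figure.** The documents give no power for the AE comparison, so only the trial's size can be checked. Inputs from 16.3: 30% v 65% response, Fisher's exact test, two-sided 0.05, 80 evaluable patients.
- Odds ratio: (0.65/0.35)/(0.30/0.70) = 4.33, as stated.
- Exact enumeration at 40 per arm gives 85.9% power, against 85% stated.
- 80/(1 − 0.20) = 100, plus 6 after the dispensing error = 106, or 53 per arm.

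These reproduce, and 53 per arm is used below.

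**2. What the AE variable contains.** Applying 10.62 and then 16.5 to a single event of one AE type:

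| Event | Submitted under 10.62? | Score in 16.5 |
|---|---|---|
| None | – | 0 |
| Grade 1, related | yes | 1 |
| Grade 1 or 2, unrelated | no | 0 |
| Grade 2, related | yes | 2 |
| Grade 3, unrelated | yes | 3 |

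An unrelated Grade 2 event ranks below a related Grade 1 event and level with no event. One grade higher, attribution no longer matters.

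**3. The baseline passages side by side.** Section 4.0 schedules an AE assessment on Day 1. Sections 6.5 and 10.61 require only nasal symptoms to be documented or graded then. Appendix I already rates dryness, pain, bleeding, scabbing and sores. Taste, throat, skin and eye effects have no required baseline record.

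**4. Size, by simulation.** All AE rates and attribution probabilities are assumptions. Test: Wilcoxon with tie correction, 53 per arm, one AE type, 3,000 trials per cell. Only Grade 1-2 events are simulated, so the figures show the effect of the filter and not of the added Grade 3-4 events.

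If a background event occurs with probability b in both arms and is attributed with probability f, the expected difference in recorded events with no spray effect is b × (f_oil − f_saline). With b = 40% and f = 40% v 20%, it is 0.40 × 0.20 = 8 percentage points. With equal f it is zero.

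Model A (background Grades 1/2 split 70/30), false-positive rate with no spray effect:

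| Background | All recorded | 30% v 30% | 40% v 20% | 50% v 20% |
|---|---|---|---|---|
| 20% | 4.3% | 5.1% | 13% | 22% |
| 40% | 5.7% | 5.2% | 24% | 42% |
| 60% | 4.7% | 5.2% | 36% | 62% |

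Model A, power for a true 20-point Grade 1 spray effect, 99.6% with no background:

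| Background | Equal 30% filter | All recorded, no baseline |
|---|---|---|
| 20% | 78% | 42% |
| 40% | 58% | 18% |
| 60% | 44% | 10% |

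Model B (true effect 15% v 2%; background Grades 1/2 split 60/40; new events 80/20):
- Power is 71% with no background. With 20% background it is 44% or 33% (30% or 50% attributed, equal in both arms). With 40% background it is 30% or 21%.
- False-positive rate at 20% and 40% background: about 5% with equal attribution; 6% and 14% with 20% v 10%; 17% and 32% with 30% v 10%; 39% and 73% with 50% v 10%.

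**5. Would recording everything be better?** Model B, 20% background. The alternative is worsening over Day 1 whatever the attribution; the comparator is the present filter at 30% attribution.

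| New chemotherapy-related events on study | All-cause worsening | Present filter |
|---|---|---|
| none | 64% | 44% |
| 10% | 29% | 37% |
| 20% | 18% | 32% |

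All-cause recording wins only if chemotherapy causes few new events of that type.

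**The case against.** The strongest reply is that the trial is randomised and double-blind, so chemotherapy toxicity balances in expectation. This stands. A reader might infer that the AE test cannot separate spray effects from chemotherapy effects, but the simulations do not support that: with equal attribution, or with everything recorded and no baseline, the false-positive rate stays near 5%.

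Three further replies also stand in part.
- The schedule says assessment, not grading, and 6.5 and 10.61 could be read as setting its scope. A reader might infer that baseline grading was planned and then withdrawn; the text does not show that. Nor does any section say that a pre-existing condition is to be counted as an on-study AE, and the pre-registration history and physical gives staff some record. What remains is that no section says what the Day 1 AE assessment records.
- The nasal symptoms most relevant to a nasal spray are rated at baseline and at Days 7 and 14, without attribution. This covers local nasal harm but not taste, throat, skin or eye effects. Appendix II item 12 asks patients in both arms about unpleasant effects, but only those from the spray, so it too requires attribution.
- The attribution filter suits a goal worded as related toxicity, and it removes noise. Step 5 confirms that dropping it can cost power.

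None of this answers the mixed scale in step 2.

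**Conclusion.** The point holds in limited form. The maximum-grade variable joins two collection rules and is not consistently ordered, which follows from 10.62 and 16.5 without any assumption. Its Grade 1-2 part rests on relatedness judgements.

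If those judgements are made equally in both arms, the test remains valid and the loss is precision: under the assumed rates, power falls from 71% to 21-44% in model B, and from 99.6% to 44-78% in model A. If attribution differs by arm, false positives rise: 6-14% for 20% v 10%, and up to 73% for 50% v 10%. The documents give no attribution rate and no evidence that blinding failed, so the larger figures are conditional. Taste and texture make unequal attribution plausible but do not establish it. Patients are asked to guess their treatment (Appendix II item 9), but no analysis of the answer is stated.

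Separately, the Day 1 assessment in 4.0 does not fit 6.5 and 10.61, and these passages need reconciling. The primary endpoint is not affected.

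**What to change.** 1. In 16.5, replace the single comparison with two between-arm analyses: (a) maximum grade of AEs at least possibly related, any grade; and (b) Grade 3+ AEs regardless of attribution. State that (a) rests on blinded attribution.
2. Reconcile 4.0 with 6.5 and 10.61. Let the Day 1 AE contact record whether the spray effects that the protocol names (bad taste, oily throat coating, burning, rash, eye irritation) are already present, and use this in (a) to identify new or worsened events.
3. Keep any all-cause Grade 1-2 comparison of these items supplementary. It should not replace (a), because new chemotherapy-related events can reduce its power (step 5).

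Cost: SAP wording, a little more analysis and a few checkboxes at a contact that is already scheduled. Patients already enrolled will have no Day 1 record, so the new-or-worsened refinement of (a) cannot be applied to them. The split into (a) and (b) can be applied to everyone.
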